3.4.2 Completion of assessments

Participants aged 12 years and older, and their parents/carers/legal guardians are expected to complete the assessments via an online survey platform (ePRO), as a starting point. For children under 12 years and CYP with neurodevelopmental conditions, such as autism, ADHD or intellectual disability, or specific learning disabilities such as dyslexia, those with English as a second language or due to personal preference, assessments may be conducted face-to-face, via video call, or through telephone interviews, depending on participant preference. This will also be offered to those where parents/carers/legal guardians have additional needs or English is not the first language. For these participant groups, where researchers are completing questionnaires directly with participants, they will be instructed to use their discretion in determining whether the informant understands the question and can provide valid responses.

All participants will be informed that a researcher can support them via telephone or video call to complete any assessments. Interpreters may be used as required. Researchers will proactively reach out to participants when the healthcare professionals or administrators in the CYPGS suggests this may be helpful, based on their clinical interactions and knowledge of the participants. These methods aim to support participation and accommodate specific needs. Participants missing a data collection window will be retained in the PATHWAYS HORIZON cohort for future data collection waves unless they withdraw, or the study ends.

4. Data Collection & Data Entry

Event/Form	Domain, information source (see legend)	Baseline	Month 12	Month 24	Annual Follow Up	Ongoing*	Estimated completion time (minutes)
Registration form & consent	R (1)	X					5
Eligibility	R (1)	X					10
Informed consent/ assent	SQ, PQ (1)	X					10
Medical history	D (6)	X					15
Demographic data	D (1)	X					2
ADHD (SNAP-IV)	PQ (5)	X					3
Autism (SCQ)	PQ (5)	X					5
Parental 'About Yourself' Questionnaire	PQ (3)	X					1
Status form	R (1)		X	X	X		1
Quality of Life (KIDSCREEN-52)	SQ, PQ (2)	X	X	X	X		7
Annual health update	SQ, PQ (6) (7)		X	X	X		6
Gender Identity Questionnaire	SQ (3), PQ**(3)	X	X	X	X		1
Social Transition Questionnaire	SQ (3)	X	X	X	X		1
Anxiety and depression symptoms (RCADS-25)	SQ, PQ (4) (7)	X	X	X	X		5
Suicide/ Self Harm (ASQ)	SQ, PQ (4) (7)	X	X	X	X		1
Gender dysphoria (UGDS-GS)	SQ (3)	X	X	X	X		3
Body image/ dysphoria (BIS-GS)	SQ (3)	X	X	X	X		3
Emotional Dysregulation (DERS)	SQ, PQ (4)	X	X	X	X		3
Sexual Attraction Questionnaire	SQ (3)	X	X	X	X		1
Romantic Relations (ALSPAC measure)	SQ (3)	X	X	X	X		5
Parental support (PAGES)	SQ, PQ (4)	X	X	X	X		3
Trauma (APCTSS)	SQ, PQ (4)	X	X	X	X		2
Emotional & Behavioural Problems (CBCL, YSR)	SQ, PQ (4)	X	X	X	X		15
Eating Problems (SCOFF)	SQ, PQ (4)	X	X	X	X		1
Withdrawal form	R (1)					X	2

LEGEND

Domains:

1=protocol adherence; 2= personal priorities and quality of life; 3= gender; 4=mental health; 5= neurodevelopmental difference; 6=physical health; 7=adverse events

Information source:

R=researcher-completed; SQ=self-reported questionnaire; PQ=parent-reported questionnaire; PQ**= parent reported questionnaire at baseline only, D=direct observation/examination

TABLE 1 SCHEDULE OF EVENTS

^{*} All ongoing forms to be reviewed and updated at each visit.

4.1.1 Enrolment visit

Participants may enrol electronically or in person, providing e-consent. Enrolment for CYP-reported measures is considered complete when there is (1) valid consent from CYP 16 years or older (2) valid consent from a parent/legal guardian of CYP under 16 years and CYP assent or (3) valid consent from a CYP under 16 years where deemed to have capacity to consent by their clinician or 4) valid consent from a Personal Consultee where CYP 16 years or older lacks capacity to consent.

4.1.2 Baseline measures

These will follow the measures indicated in the Schedule of Events.

4.1.3 Annual follow-up visits

Follow up data will be collected as per the Schedule of Events in Table 1 above for the relevant yearly visit and ongoing section. At each follow up timepoint, a status form is completed in the study database to indicate whether the participant remains in the CYPGS.

4.2 DATA ENTRY

4.2.1 *Medrio EDC*

Authorised staff at sites will transcribe baseline and follow up participant data from source data worksheets (SDWs) to the Medrio Electronic Data Capture (EDC) system by going to www.ctu.co.uk and clicking the link to access Medrio. A full audit trail of data entry and any subsequent changes to entered data will be automatically date and time stamped, alongside information about the user making the entry/changes within the system.

Study site staff will be delegated by the site PI to access the EDC system via a Study Site Delegation Log. The request for user access must go to the Trial Manager (TM), who will submit user requests for all sites to the KCTU team upon receipt of completed Study Site Delegation Logs. Requests for user access will be processed within a maximum of 5 working days.

Training videos for site data entry staff, site monitors and trial co-ordinators are available at www.ctu.co.uk under the 'Training' section. Users can self-register and should select the Medrio related training videos.

4.2.2 Medrio eConsent

The Medrio electronic consent (eConsent) module will be used by site staff to document informed assent/consent from participants and parents/carers/legal guardians.

4.2.3 Medio ePRO

The electronic patient reported outcomes (ePRO) module of Medrio will be used by participants to complete self-reported and parent-reported measures outlined in the Schedule of Events above. Participants will be set up on the ePRO module following informed consent.

4.3 DATA COLLECTION

Participant self-report measures should ideally be completed independently, as indicated in the instructions to participants at the top of each measure on ePRO.

Please refer to Annex 2 for individual schedule of events for CYP participants, parent participants, and clinician/researcher collected information.

4.3.1 REGISTRATION FORM AND CONSENT

Upon the participant being added into Medrio EDC, the system will assign a unique study PIN to be used for the participant throughout the study. When valid informed consent has been provided

via the Medrio eConsent module (see section 5.1.2), the study site staff will complete the Registration Form for the participant in the Medrio EDC system using participant initials, date of birth, date of consent, and version number of the assent/consent form.

4.3.2 ELIGIBILITY

CRF confirms the CYP has been offered/attended initial assessment appointment at a CYPGS and their informed assent/consent has been obtained. This will include the date of referral to the CYPGS, date referral accepted, date of first appointment, CYPGS for care confirmation that first appointment attended. The form will also indicate any special procedures to be followed, e.g., if self/parent-report measures should be completed by the researcher. It will designate adults with parental responsibility for CYP under 16 years.

4.4 MEASURES/DATA FORMS

All validated measures where applicable have been adapted for digital use and display

4.4.1 Baseline only

4.4.1.1 Medical history

At the initial assessment in the CYPGS as part of routine care, clinicians will obtain structured information on participants' medical history as per the domains outlined below. For research sites using the clinical record system EPIC, this will form part of the electronic patient record, which can be extracted and transcribed into the study database. For research sites not using EPIC, a Source Data Worksheet (SDW) will be provided to capture the relevant information.

Medical History Domains:

- 1. Family Context
- 2. Developmental History
- 3. Physical Health
- 4. Mental Health and Risk
- 5. Adverse childhood experiences
- 6. Safeguarding
- 7. Gender Development and Experiences
- 8. Sexual Development, Knowledge and Sexual Orientation
- 9. Education, Peer Relationships, and Social Context
- 10. Additional Information. Clinical Judgements Impact assessments and clinical evaluation for various aspects of the CYP's development and wellbeing; Parental Support Judgements on the level of positive parental support and any conflicts between parents/carers/legal guardians or between parents/carers/legal guardians and the CYP.

4.4.1.2 **Demographics**

This form will include participant date of birth, country of birth, participant ethnicity, participant address with full post code, parental marital status and parents/carers/legal guardians with whom participant is living. Only the date of birth and ethnicity will be entered into Medrio EDC. (Note for clarity, this is different from the Registration form described above.)

4.4.1.3 Swanson, Nolan, and Pelham-IV (SNAP-IV)

The SNAP-IV¹⁵ is an 18-item scale used to assess symptoms of ADHD, across two subscales: inattention and hyperactivity/ impulsivity. Parents/carers/legal guardians will be asked to rate how often their child endorses each item on a 4-point Likert scale (0= not at all; 3= very much). We will obtain parent report questionnaires only. Duration: 3 minutes.

4.4.1.4 Parental 'About Yourself' Questionnaire

The 'About Yourself 'questionnaire is a non-validated 2-item self-report measure evaluating gender identity and sex assigned at birth of the parent; these were based on questions from the UK based National LGTB Survey ¹⁶. The Parent will be asked 'Do you identify' as: 'woman/girl', 'man/boy', 'transwoman/transgirl', 'transman/transboy', 'non-binary/genderqueer/agender/gender fluid', 'don't know', 'prefer not to say', 'other'. The second question asks; 'What was your sex assigned at birth?', with response categories of 'female', 'male', 'don't know', and 'prefer not to say'. This will be measured at baseline only. Duration: 1 minute.

4.4.1.5 Social Communication Questionnaire (SCQ)

The SCQ is a screening tool used to assess traits of autism spectrum disorder (ASD)¹⁷. The SCQ current version measures symptoms over the previous 3-months. The measure comprises 40 yes/no questions and will be completed by parents/carers/legal guardians only. Total scores range between 0 and 39, and a clinical cut-off of 15 is used to detect probable ASD. The measure has been adapted to include gender neutral language. Duration: 5 minutes.

4.4.2 Longitudinal/outcome -baseline and annual follow-up assessments

Where possible scales should be completed in the order as they are listed below.

4.4.2.1 KIDSCREEN-10 (PRIMARY OUTCOME)

The KIDSCREEN-10¹⁸ is a 10-item questionnaire designed to evaluate the subjective health and well-being of CYP using a single factor general health-related quality of life (HRQoL). All 10-items are included within the KIDSCREEN-52. The KIDSCREEN-10 will therefore be administered as part of the KIDSCREEN-52 described below. Primary outcome scores will be obtained separately, using the single factor structure of the KIDSCREEN-10.

4.4.2.2 **KIDSCREEN-52**

The KIDSCREEN-52 ¹⁸ is a 52-item questionnaire designed to evaluate the subjective health and well-being of CYP. It assesses ten dimensions: physical activities and health, feelings, general mood, about yourself, free time, family and home life, money matters, friends, school and earning, bullying. Items are scored using a 5-point Likert scale (e.g. 1= not at all; 5= extremely). Higher scores indicate higher health related quality of life and wellbeing. Both a self-report version for CYP and a parent-report version will be administered. The parent-report measure has been adapted to include gender neutral language. Duration: 7 minutes.

4.4.2.3 Gender Identity

The gender identity questionnaire for CYP is a 2-item self-report measure developed for PATHWAYS with the PATHWAYS advisory group. In this measure, gender identity is defined as the gender that someone feels and knows themselves to be. CYP will be asked 'What best describes your gender identity?' to assess their current expression of gender identity. The response options will include 'definitely a boy', mainly a boy', 'in the middle', 'definitely a girl', 'mainly a girl', 'neither a boy or girl', 'not sure' and 'none of the above'. CYP over 12 years will additionally be asked about gender identity labels, specifically 'Are there other words that you use to describe your gender identity? (select all that apply), 'cisgender', transgender', 'non-binary', 'agender', 'genderfluid', 'genderqueer', 'two-spirit' and 'other'. Duration: 1 minute.

4.4.2.4 Social Transition Questionnaire

The Social Transition Questionnaire is a single-item, novel, self-report measure designed to assess the extent to which participants have socially transitioned across different everyday settings. Social transition refers to changes in presentation, such as appearance, clothing, name, or behaviour, that align more closely with an individual's experienced gender. Participants are asked: "Have you socially transitioned in any of the following settings?", followed by a checklist of five settings: Home, School, With Friends, Online, and Any Other Setting (e.g., holiday). For each setting, participants are instructed to select one of three response options: "Most or all the time", "Sometimes", or "Never". This measure has been developed specifically for the PATHWAYS study in consultation with stakeholders and community advisors. Duration: 1 minute.

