3.1 Participants

Participants will include CYP of any age referred to the CYPGS, along with their parent(s), caregiver(s), or legal guardian(s) following acceptance of the referral. CYP may be seen in the service up to age 18 years, at which point they are referred to adult Gender Services. Referrals to the CYPGS may be made by an NHS-commissioned secondary care level paediatric service or CYP mental health service. For a referral to be accepted, it must indicate that the CYP is experiencing concerns or distress related to their gender identity. The absence of a lower age limit applies only to the HORIZON study and not to other studies in PATHWAYS which have a greater focus on GnRHa. The purpose of the HORIZON study is to provide a comprehensive description of the presenting characteristics and developmental trajectories of all CYP presenting to the service, in order to improve care for the entire population.

Only CYP and their parents/carers/legal guardians who attend a first assessment appointment in the CYPGS will be included. CYP remain eligible to participate in the study even after discharge from the services, including those who transition to adult services. All CYP and their parents/carers/legal guardians will be followed up annually, even if they no longer remain within the service and/or have been discharged, unless they withdraw from the study.

CYP and their parents/carers/legal guardians who attended a first appointment in the new CYPGS and were discharged prior to the study onset will also be contacted to provide them with the opportunity to participate.

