4.4.2.9 Body Image Scale – Gender Spectrum (BIS-GS)

The BIS-GS ²³ is a gender neutral version of the Body Image Scale (BIS)²⁴ used to assess an individual's relationship with their body. The scale consists of 33 items. Respondents rate their feelings towards each body part using a 5-point Likert scale (1= very satisfied; 5= very dissatisfied). Respondents also rate whether they would want to change each body part if it was possible through medical or surgical treatment using a yes/no response. Each item includes a 'don't have' response if the individual does not have that body part (e.g. vagina). Respondents are then asked to rate how they feel about not having that body part using the same 5-point Likert scale, and to indicate whether they would want to change this. Higher scores indicate greater body dissatisfaction. Only CYP self-report versions will be obtained. Duration: 3 minutes.

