8.6 METHODS FOR ADDITIONAL ANALYSES (E.G. SUBGROUP ANALYSES)

The below CYP subgroups are planned to be used as subgroup analyses.

- Birth-registered sex
- Age at referral
- Neurodevelopmental and mental health diagnoses
- Social transition status
- Adverse life experiences

These analyses will be carried out using interaction terms in mixed models, and stratified analyses to compare separate analyses within each subgroup. Further subgroup analyses and analysis specifications will be detailed in the statistical analysis plan.

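### The Social Transition Questionnaire has no not-applicable response, so *Never* at School is ambiguous for young people who are not at school

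*Protocol*

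**What the plan says.** Section 4.4.2.4 of the protocol describes a novel self-report item developed for PATHWAYS. The stem asks "Have you socially transitioned in any of the following settings", followed by Home, School, With Friends, Online and Any Other Setting. The answering rule is "For each setting, participants are instructed to select one of three response options": *Most or all the time*, *Sometimes* or *Never*. No response is listed for a setting the respondent is not in. Table 1 and Annex 2 (Table 2) schedule the item at baseline and at every annual follow-up.

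Section 3.1 sets the age range: "Participants will include CYP of any age referred to the CYPGS". Participants are seen in the service up to 18 and are followed annually "even if they no longer remain within the service and/or have been discharged", including after a move to adult services. Section 2 gives 3.5 years of recruitment within a study of about 5.5 years.

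Section 8.2 lists the questionnaire as a secondary outcome for descriptive display only. Section 8.6 names "Social transition status" as a subgroup variable, to be used in interaction terms and stratified analyses.

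**The concern.** A respondent with no school to attend has no response that says so. This could be a school leaver, a home-educated child or a child below school age. *Never* is available to them, but it is also the answer of someone who attends school and has not transitioned there. The two states differ in substance and would share a code.

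Two uses of the item are exposed. The first is the wave-by-wave description of transition at school, where leaving school could look like a reduction in transition. The second is the subgroup in section 8.6. If it draws on the School answer at follow-up, membership would depend partly on age or on not being at school.

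The same battery provides for inapplicable items elsewhere. For the BIS-GS, section 4.4.2.9 says "Each item includes a 'don't have' response if the individual does not have that body part".

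**Working it through.** The protocol gives no figure for this item, so there is nothing to reproduce. The check has three parts.

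**1. Can participants be past school age while still answering?** Recruitment ends at 3.5 years of 5.5, so the last recruits have 5.5 − 3.5 = 2.0 years of possible follow-up and every entrant can reach Month 24. The earliest recruits can reach Month 60, since 5.5 years is 66 months. Anyone aged 16 or over at entry is at least 18 at Month 24, and anyone aged 14 or over at entry is at least 18 at Month 48. Leaving school during follow-up is therefore built into the design. The protocol gives neither the entry-age distribution nor the share at school.

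**2. Could the analysis separate the two meanings of *Never*?** As described:
- Education is a domain of the baseline medical history (section 4.4.1.1, domain 9), collected at baseline only.
- The Annual Health Update (section 4.4.3.1) covers height, weight, medication, diagnoses and health-care use.
- The status form (sections 4.1.3 and 4.4.3.2) records status in the study and in the service.
- The KIDSCREEN-52 (section 4.4.2.2) has a school dimension, but it is described as rating quality of life, not recording attendance.

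None is described as recording school attendance at follow-up. Date of birth is held (sections 4.4.1.2 and 5.2), so age is known, but age is only a proxy for attendance.

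**3. How large could the effect be?** Let p be the true share transitioned at school among attenders, held constant; s the share of respondents not at school; and f the share of those who tick *Never*. All three are assumptions.
- If the other non-attenders leave the item blank, the reported share is p(1 − s) / [(1 − s) + s·f].
- If the others answer as attenders do, for example about past schooling, it is p(1 − s) + s(1 − f)p = p(1 − s·f).

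With p = 60%:

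| s | f = 0 | f = 0.5 (others blank / others answer as attenders) | f = 1 |
|---|---|---|---|
| 10% | 60% | 57% / 57% | 54% |
| 30% | 60% | 49% / 51% | 42% |
| 50% | 60% | 40% / 45% | 30% |

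Worked cell, s = 30% and f = 0.5: 0.42 / (0.70 + 0.15) = 0.494 with blanks; 0.60 × (1 − 0.15) = 0.51 otherwise. At f = 1 both formulas reduce to p(1 − s). At s = 50% and f = 1, p = 40% gives 20% and p = 80% gives 40%.

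A downward drift needs two things: f above zero, and s rising between waves. If s is constant, the result is an error in level without a trend. With a not-applicable response used as intended and attenders as the denominator, the reported share equals p at every wave.

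**The case against.** The strongest reply is that the protocol does not say what a non-attender's answer will be. An instruction to select an option is not a mandatory field or a coding rule. The stem has no recall period, so someone who was fully transitioned at school and has since left could truthfully give the same answer again. Others may skip the item or count college as school. All of this stands. It rules out the stronger reading a reader might infer, that non-attenders are recorded as *Never* and that transition at school will appear to fall. It also confirms that the answer is undefined for this group, which is the point made here.

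The planned use is modest. The outcome is descriptive only, so no model of a school trajectory is planned. Section 8.6 does not fix how or when subgroup status is derived and leaves specifications to the SAP. A subgroup taken at baseline, or defined as transition in any setting, would be little affected. This too stands, and it limits the subgroup concern to a definition that uses the School answer at follow-up.

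Age is a fixed effect in the models (section 8.4.1). That helps in part, but it neither corrects a misclassified subgroup nor touches the descriptive tables.

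The BIS-GS comparison is also limited. Its extra response leads to a further rating and does not remove the person from a denominator. It shows that inapplicable items were considered elsewhere, and no more.

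**Conclusion.** The ambiguity is real and lies in the instrument as the protocol specifies it. School is asked of every respondent, no response covers being out of school, follow-up runs past school age, and no described follow-up form would let the analysis separate the two meanings of *Never*.

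Its effect is possible, not established. With a true share of 60% and half of respondents out of school, the reported share lies anywhere from 60% to 30%, depending wholly on how non-attenders answer. A steep decline quoted as a single figure would rest on assuming that every leaver ticks *Never*, which the documents do not support. Nor do they show that the section 8.6 subgroup is biased, since its derivation is not given.

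This is a minor but worthwhile correction to a novel item, and it should be made early because the missing information cannot be reliably recovered later.

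**What to change.** Either of two changes is enough:
- add a response such as *Not applicable / not in this setting* for each of the five settings, and report each setting among those to whom it applies; or
- record school attendance at each wave and report the School answer among attenders only.

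The cost is a small ePRO update, either to an item developed in-house or as one extra attendance question. Forms already completed will lack the information and cannot be reliably corrected afterwards, because school status at follow-up is not described as collected. School responses from those forms should be tabulated by age, using the date of birth already held, with a note that *Never* may include respondents not at school.
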